6.3.4.2. Analysis

Summary statistics of actual values and change from baseline to each scheduled visit will be provided by treatment group.

Analysis of the change from baseline to each scheduled visit will use the same MMRM model described in Section 6.3.3.2 with the exception of inclusion of sex and height in the model. A line graph will be provided for the LS mean change from baseline over time (at each visit).

AQLQ +12 at Week 52 will additionally be examined for the selected subgroups defined in Section 3.4. The analysis of subgroups will use a MMRM model similar to the one described above. Subgroups will be presented graphically using forest plots.

The proportion of patients achieving an increase of ≥ 0.5 in the AQLQ +12 score from baseline to each scheduled visit will be summarized. A stratified (based on randomization strata) Cochran-Mantel-Haenszel (CMH) test will be used to analyze the proportion of patients achieving an increase of ≥ 0.5 in the AQLQ +12 score from baseline to Week 52.

6.3.5. ACQ-6

6.3.5.1. Variable Definition

The ACQ-6 was developed to measure asthma control. The ACQ-6 is a 6-item instrument; each item is scored on a scale of 0 to 6 (higher scores are an indication of poorer asthma control). At weeks 2, 4, 8, 12, 16, 20, 24, 28, 32, 36, 40, 44, 48, and 52, the patient answers each of the 6 questions, identifying the response that best describes how the patient has been during the past week.

6.3.5.1.1. Missing data handling and total score calculation

The overall score of the ACQ-6 is derived as the average of the individual item scores; the analysis will be based on the available data.

For incomplete data, the following rules will apply:

1. Total score for the visit will not be calculated if Question 1 is left blank, irrespective of the completion of the remaining questions.
2. A missing score on post screening questionnaire for Questions 2-6 will be imputed based on the total scores from the previous visit, as long as at least 3 out of the 5 questions have responses for the current visit (ie, at least half of the remaining questions are answered).

The formula is: (total sum of non-missing scores for the current visit / total sum of scores for the previous visit for questions answered for the current visit) * (score for the missing question on the previous visit)

3. Total score at screening will not be calculated if Question 1 or two or more among Questions 2-6 is left blank. A missing score for Questions 2-6 at screening will be replaced by an average of the available scores.

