### **6.5. Asthma Control Questionnaire**

The ACQ is a validated asthma assessment tool that has been widely used (Juniper et al 1999). Six questions are self-assessments (completed by the patient). Each item on the ACQ has a possible score ranging from 0 to 6, and the total score is the mean of all responses (Appendix C).

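### The ACQ-6 missing-item formula has no upper limit and no zero-denominator rule, so as written it can give an item score above the 0–6 scale or no value at all

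*SAP*

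**What the plan says.** SAP 6.3.5.1 states that "each item is scored on a scale of 0 to 6", with higher scores meaning poorer control. Protocol 6.5 gives the same range: "Each item on the ACQ has a possible score ranging from 0 to 6". SAP 6.3.5.1.1 then says: "The overall score of the ACQ-6 is derived as the average of the individual item scores".

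That section has three rules for incomplete forms.

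- Rule 1: there is no total if Question 1 is blank.
- Rule 2 (after screening): a missing item among Questions 2–6 is imputed "as long as at least 3 out of the 5 questions have responses for the current visit". The imputed value is the "total sum of non-missing scores for the current visit", divided by the "total sum of scores for the previous visit for questions answered for the current visit", times the "score for the missing question on the previous visit".
- Rule 3 (screening only): "A missing score for Questions 2-6 at screening will be replaced by an average of the available scores". No total is given if two or more of Questions 2–6 are blank.

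Rule 2 states no upper limit. It says nothing about a zero denominator or about a previous item score that is itself missing, and no other section supplies these. SAP 6.3.1 lists change in ACQ-6 at week 52 third among the secondary endpoints in the fixed sequence. SAP 6.3.5.2 uses the same score for a responder analysis, defined as a reduction of at least 0.5 from baseline.

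**The concern.** A scoring rule should return a value on the instrument's scale for every form that it admits. Rule 2 does not. A patient who worsens between visits can be given an item score that no respondent could record, and the total is inflated with it. A patient whose previous answers were all 0 on the items answered now gets no value at all, and the SAP does not say what the programmer should do.

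The rule covers every post-screening form, including baseline/DoR and week 52. An off-scale score could therefore enter the repeated-measures model as an outcome or as the baseline covariate, and could enter the responder count. If ACQ-6 is not significant, the six secondary endpoints listed after it are not interpreted inferentially.

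**Working it through.** **Inputs.** Items run from 0 to 6 (SAP 6.3.5.1, Protocol 6.5). The total is the mean of six items. Question 1 and at least three of Questions 2–6 must be answered, so at most two items are imputed. The SAP states no numerical result for this rule, so there is no figure to reproduce.

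**Notation.** S is the sum of the items answered now, P the previous-visit sum of the same items, and m the previous score of the missing item. Rule 2 gives: imputed item = (S / P) × m.

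**Above the scale.** The item exceeds 6 when S/P > 6/m. For m = 1, 2, 3, 4, 5, 6 the ratio must exceed 6, 3, 2, 1.5, 1.2 and 1. With one missing item, the total is (S + imputed item) / 6:

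| P | S | m | Imputed item | Total as written | Total, item capped at 6 |
|---|---|---|---|---|---|
| 3 | 15 | 2 | 15/3 × 2 = 10 | 25/6 = 4.17 | 21/6 = 3.50 |
| 4 | 13 | 3 | 13/4 × 3 = 9.75 | 22.75/6 = 3.79 | 19/6 = 3.17 |
| 1 | 4 | 2 | 4/1 × 2 = 8 | 12/6 = 2.00 | 10/6 = 1.67 |
| 5 | 18 | 2 | 18/5 × 2 = 7.2 | 25.2/6 = 4.20 | 24/6 = 4.00 |
| 9 | 19 | 3 | 19/9 × 3 = 6.33 | 25.33/6 = 4.22 | 25/6 = 4.17 |

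With one item missing, leaving the scale adds (imputed item − 6)/6 to the total. In the first row this is (10 − 6)/6 = 0.67. It exceeds 0.5 only if the imputed item exceeds 9. The total can also leave the scale: the algebraic extreme for one missing item is S = 30, P = 1, m = 6, giving an item of 180 and a total of (30 + 180)/6 = 35.

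**Undefined.** P = 0 whenever every item answered now was scored 0 at the previous visit. If the current answers are also all 0, the formula is 0/0. If the previous scores were (0,0,0,0,0,2) and the current ones are (1,1,1,0,0,missing), it is 3/0 × 2.

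**Baseline/DoR.** The previous ACQ form is the screening form, where a score of at least 1.5 is required (Protocol 4.1, criterion d), so the six items sum to at least 1.5 × 6 = 9. With one item missing, P is at least 9 − 6 = 3 and the formula is defined. It can still exceed 6: S = 15, P = 3, m = 6 gives 30. With two missing, P can be 0, because 9 is less than 2 × 6 = 12.

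**Responder status, first row.** A responder needs baseline minus total of at least 0.5. With the capped total this requires a baseline of at least 3.50 + 0.5 = 4.00, and with the uncapped total at least 4.17 + 0.5 = 4.67. Status differs only for baselines from 4.00 to just under 4.67.

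**The case against.** Much of the case against a stronger reading stands.

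- A reader might infer that the formula breaks down for well-controlled patients in general. It does not. It is undefined only when the previous scores on all items answered now were exactly 0. Low but non-zero scores give a defined value.
- A reader might infer a bias between arms, because an effective drug produces more well-controlled patients. The two failures point to different patients: one needs previous zeros, the other needs marked worsening between visits. The documents support no direction or size of effect on the treatment difference.
- A reader might measure the first example against the mean of the answered items (15/5 = 3.00, a total of 18/6 = 3.00) and report a defect of 1.17. Only 0.67 of that comes from leaving the scale. The other 0.50 is a preference between two imputation methods. The example is also extreme, a fivefold rise between adjacent visits.
- A reader might object that an item previously scored 0 is imputed as 0 however much the patient has worsened. Any proportional, item-specific rule behaves this way, and the mean has the opposite weakness of ignoring the patient's usual level on that item.
- A reader might want the screening rule used throughout. That goes beyond the evidence. Rule 3 gives no total with two or more blanks, whereas rule 2 allows two. The questionnaire sample in Protocol Appendix C is not visible in the available text, so it cannot be checked whether the ratio is the instrument's own scoring instruction.

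It can also be said that an undefined item would simply leave the total missing. SAP 6.3.5.1.1 refers to available data, SAP 4.4 plans no estimation of missing data outside the primary analysis, and the model would use the patient's other ACQ-6 visits, of which 14 are scheduled after baseline. That is a plausible reading of the undefined case, but the SAP does not state it. It also does nothing for the above-scale case, where a value is computed and enters the analysis.

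**Conclusion.** The rule is wrong as written, with low severity. Both defects follow from the formula and the 0–6 item range alone. The imputed item leaves the scale when S/P > 6/m, and the item is undefined when P = 0. In the illustrative case the total is 4.17 rather than 3.50, an excess of 0.67. Milder cases add as little as 0.06, which is (6.33 − 6)/6.

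The practical effect cannot be sized. It needs a skipped item together with a particular pattern of previous scores, and the documents give no item-missingness rate. The form is completed in clinic, and Protocol 13.1 names a tablet as a data source, so skipped items may be rare. Few forms may be affected, and no bias between arms is shown. ACQ-6 is interpreted inferentially only if the primary endpoint, FEV1 and AQLQ +12 are all significant first.

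**What to change.** Keep the ratio formula in SAP 6.3.5.1.1 rule 2 and add one sentence: the imputed item is truncated to the range 0–6, and if the denominator is 0 or a previous-visit score needed by the formula is unavailable, the missing item is replaced by the mean of the items answered at that visit. Only the upper limit will ever bind, because all terms are non-negative.

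The conditions on Question 1 and on three of the other five questions stay as they are. With two items missing, the fallback applies the mean where rule 3 would give no total, so the sentence should say that this is intended. A cross-reference in SAP 4.4 would reconcile its statement on not estimating missing data with this item-level rule.

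The cost is that sentence and a minor programming change, with no new data. It should be settled before unblinding, so that the choice is not made with treatment known.

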6.3.5.2. Analysis

Summary statistics of actual values and change from baseline to each scheduled visit will be provided by treatment group.

Analysis of the change from baseline to each scheduled visit will use the same MMRM model described in Section 6.3.3.2 with the exception of inclusion of sex and height in the model. A line graph will be provided for the LS mean change from baseline over time (at each visit).

ACQ-6 at Week 52 will additionally be examined for the selected subgroups defined in Section 3.4. The analysis of subgroups will use a MMRM model similar to the one described above. Subgroups will be presented graphically using forest plots.

The proportion of patients achieving a reduction of ≥ 0.5 in the ACQ-6 score from baseline to each scheduled visit will be summarized. A stratified (based on randomization strata) CMH test will be used to analyze the proportion of patients achieving a reduction of ≥ 0.5 in the ACQ-6 score from baseline to Week 52.

6.3.6. SGRQ

6.3.6.1. Variable Definition

St. George's Respiratory Questionnaire (SGRQ) is a health status survey specific for chronic obstructive pulmonary disease and other respiratory diseases. The SGRQ consists of 2 parts: Part 1 produces a symptom score and Part 2 produces an activity and impacts score. A total score is also calculated. The SGRQ is administered as a self assessment at weeks 32 and 52.

The questions in the SGRQ are divided into 3 domains:

- Symptoms: Questions 1-8
- Activity: Questions 11, 15

- Impacts: Questions 9-10, 12-14, 16-17

The SGRQ requests a single response to each of Questions 1-10 and 17; whereas Questions 11-16 each request multiple responses, resulting in a total of 50 responses across the questionnaire.

6.3.6.1.1. Missing data handling and total score calculation

Each questionnaire response has a unique empirically derived ‘weight’ (the lowest possible weight is 0 and the highest is 100). The weights associated with each response is provided in [Appendix C](#). Derivation of each domain and total score is as follows:

1. The weights for all items with a positive response are summed.
2. The weights for missing items are deducted from the maximum possible weight for each domain (or total) score. The maximum possible weights for each domain and total score are 662.5 (symptoms), 1209.1 (activity), 2117.8 (impacts), and 3989.4 (total).
3. The score is calculated by dividing the summed weights (from Step 1) by the adjusted maximum possible weight for the domain or total score (from Step 2) and expressing the result as a percentage:

$$\text{Score} = 100 \times (\text{Sum of weights from positive items in the domain (or total)} / \text{Sum of weights for all items in the domain (or total)})$$

Thus, scores are expressed as a percentage of overall impairment, where 100 represents the worst possible health status and 0 represents the best possible health status. The questionnaire requests a single response to each of Questions 1-10 and 17. If multiple responses are given to any one of these questions, then the weights for the positive responses for that question will be averaged.

[figure not shown]
A score will only be calculated if at least 75% of the responses for the total and/or domain score are non-missing for a given visit. If more than 25% of the questions are missing, then the total and/or domain score will be considered missing for that visit. For the symptoms domain (8 total responses), this threshold translates to a maximum of 2 missed responses that can be tolerated. For the activity domain (16 total responses), a maximum of 4 missed responses can be tolerated. For the impacts domain (26 total responses), a maximum of 6 missed responses can be tolerated. For the total score (50 total responses), a maximum of 12 missed responses can be tolerated.

6.3.6.2. Analysis

Summary statistics of actual values and change from baseline to each scheduled visit will be provided by treatment group.

Analysis of the change from baseline to each scheduled visit will use the same MMRM model described in Section [6.3.3.2](#) with the exception of inclusion of sex and height in the model.

The proportion of patients achieving a reduction of ≥ 4 in the SGRQ score from baseline to each scheduled visit will be summarized. A stratified (based on randomization strata) CMH test will be used to analyze the proportion of patients achieving a reduction of ≥ 4 in the SGRQ score from baseline to Week 32.

6.3.9. Asthma Control Diary

6.3.9.1. Variable Definition

6.3.9.1.1. Asthma symptom scores

The asthma symptom score will be determined every morning and evening by the patient and recorded in the daily asthma control diary. The asthma symptom score is used to measure how much patients are bothered by their asthma symptoms. Asthma symptom score will be rated on a scale, with higher scores indicating more severe symptoms. The daytime asthma symptom score (range: 0-5) will be assessed in the evening and indicate how the patient felt earlier that same day. The nighttime asthma symptom score (range: 0-4) will be assessed in the morning and indicate how the patient felt during the previous night. Total asthma symptom score (range: 0-9) will be derived as the sum of the daytime and nighttime symptom scores.

6.3.9.1.2. Total reliever use

The number of times SABA reliever therapy is used will be recorded by the patient, once in the morning and once in the evening. Total reliever use will be derived as the sum of the morning and evening counts.

6.3.9.1.3. Nighttime awakenings

Nighttime awakenings will be recorded daily in the morning to indicate whether the patient was awakened during the previous night due to asthma. An awakening-free night (y/n) is defined as a night during which the patient did not experience a nighttime awakening.

6.3.9.1.4. Peak expiratory flow

Peak expiratory flow (PEF) is the maximum speed of exhalation, measured by a PEF meter. Morning (AM) and evening (PM) ambulatory PEF will be measured daily by the patient and the maximum of 3 separate readings will be recorded in the asthma control diary.

6.3.9.1.5. Asthma control days

An asthma control day (y/n) is defined as a day on which the patient used ≤ 2 puffs of inhaled SABA therapy, had no nighttime awakenings, and experienced no CAEs or moderate exacerbations.

6.3.9.2. Analysis

Compliance with the daily diary assessments will be derived for each patient as an additional measure of protocol adherence. A diary compliant day will be defined as a day with non-missing values for all diary assessments, including AM/PM asthma symptom score, [REDACTED],

[REDACTED]. Diary compliance will be derived as a percentage over the treatment period:

- $\text{Diary compliance (\%)} = 100 \times (\text{total number of diary compliant days} / \text{total number of days during the treatment period})$

The treatment period for diary compliance extends from the first day of study drug to the last day of study drug. Note that, in this analysis, missing data will be treated as non-compliant (eg, if compliance cannot be assessed for a given day due to missing data, then the day will not be counted as a diary compliant day).

[REDACTED]

A weekly average of the daily diary measures ([REDACTED], total asthma symptom score, and [REDACTED]) will be derived (see [Table 3](#) for the definition of analysis days for diary data). The average will be calculated as the sum of all values divided by the number of non-missing assessments. There will be no imputation of missing data. At least 4 of the 7 measurements need to be recorded for a week to be included in the analysis; otherwise the week will be treated as missing.

[REDACTED] and asthma control days will be derived and analyzed as percentages over the relevant analysis period, derived as:

- $\text{Asthma control days (\%)} = 100 \times (\text{total number of asthma control days} / \text{total number of days during the analysis period})$

[REDACTED]

The analysis periods are as defined in [Section 6.3](#). Note that, in this analysis, missing data will be treated as non-responders (eg, if asthma control cannot be assessed for a given day due to missing data, then the day will not be counted as an asthma control day).

Summary statistics of actual values and change from baseline to each week will be provided by treatment group.

Analysis of the change from baseline to each week will use a similar MMRM model as described in [Section 6.3.3.2](#) with the exception of inclusion of sex and height in the model.

Analysis of the percentage of [REDACTED] and percentage of asthma control days will be performed using an analysis of variance (ANOVA) model with fixed effects for treatment, age group, and blood eosinophil counts at enrollment.

A line graph presenting the LS mean change from baseline over time (at each week) will be provided for [REDACTED] total asthma symptom score, and [REDACTED] by treatment group.

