**3.16.3.1.2. Other On-Treatment Visits (Visits 4 through 17 [EOT])**

During the double-blind treatment period, patients will return to the study center at week 2 and week 4 and then once every 4 weeks ( $\pm 7$  days) thereafter (relative to baseline/DoR) for administration of study drug and assessments until 4 weeks after the final administration of study drug (week 52 or early withdrawal).

The following procedures/assessments will be performed before administration of study drug at each of these visits, unless otherwise indicated:

- Perform urine pregnancy testing (female patients who are not 2 years postmenopausal or surgically sterile only) (excluding week 2 [visit 4]).
- Perform hematology tests (weeks 2, 4, 8, 12, 16, 32, and 52 or early withdrawal only).
- Perform serum chemistry tests (weeks 16, 32, and 52 or early withdrawal only) (a sample for CPK measurement only, will also be collected on weeks 2, 4, 8, 12, and 20).
- Perform full physical examination (week 52 or early withdrawal only).
- Perform brief physical examination (excluding week 52 or early withdrawal).
- Perform vital signs measurements (includes systolic and diastolic blood pressure, pulse, body temperature, and respiratory rate).
- Measure height and weight (weeks 24 and 52 or early withdrawal only; patients 12 to 21 years of age only).
- Perform ECG (week 24, 36, and 52 or early withdrawal only).
- Perform concomitant medication inquiry.
- Perform adverse event inquiry.
- Complete asthma-specific tests.
  - If patient has withheld inhaled long acting and short-acting bronchodilators for the requisite time period, perform pre-bronchodilator spirometry, including FEV1, FVC, and FEF25%-75% (weeks 2, 4, 8, 12, 16, 32, and 52 or early withdrawal only).
  - Perform post-bronchodilator spirometry, including FEV1 (weeks 16, 32, and 52 or early withdrawal only). If inhaled bronchodilators were used within the specified withhold window, lung function testing should be delayed until the withhold time is met if feasible, or the visit should be rescheduled. If neither option is feasible for the patient, the test may proceed and the deviation recorded.
  - Collect PEF meter (week 52 or early withdrawal only).
  - Collect and review daily asthma control diary, and reinforce diary and PEF compliance (excluding week 2).
  - Complete the ACQ-6 (may be completed after study drug administration during the 1-hour observation period.)

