For summaries of diary data (eg, rescue medication use, asthma symptom score), the day used for analysis will consist of the evening assessment for the day and the morning assessment for the following day, as illustrated in Table 3. Weekly average data will be generated using 7-day windows derived based on these analysis days.

Table 3: Definition of Analysis Days for Diary Data

Study Period	Diary Day	Study Day ^a	Time Point	
Baseline	Day -7	-7	PM	
		-6	AM	
	Day -6	-6	PM	
		-5	AM	
	Day -5	-5	PM	
		-4	AM	
	Day -4	-4	PM	
		-3	AM	
	Day -3	-3	PM	
		-2	AM	
	Day -2	-2	PM	
		-1	AM	
	Day -1	-1	PM	
		1 (pre-dose)	AM	
	Treatment	Day 1	1	PM
			2	AM
Day 2		2	PM	
		3	AM	
Day 3		3	PM	
		4	AM	
...		..	PM	
		..	AM	
Day 364		364	PM	
		365	AM	

^a Study Day 1 denotes the first dose of study drug; Study Day -1 is the day prior to the first dose of study drug.

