6.3. Secondary Efficacy Variable(s) and Analysis

As described previously in Section 4.5, an on-treatment approach will be adopted as the primary analysis for the efficacy variables assessed by-visit. In this analysis, the treatment period will be defined from the first dose of study drug to the end of treatment (week 52) visit for patients who completed treatment and from the first dose of study drug to the last dose of study drug (+4 weeks) for patients who discontinued treatment early. Measurements collected outside of these defined timeframes will be excluded from the analyses and endpoint will be defined within these timeframes. All results will be included in the patient listings. For selected key variables, additional sensitivity analyses may also be performed in which all post-baseline measurements collected during the study will be included and endpoint will be defined within this extended timeframe.

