6.3.1. Secondary Variables

The secondary efficacy endpoints are as follows:

- change in pre-bronchodilator FEV₁ from baseline/DoR at week 52
- change in Asthma Quality of Life Questionnaire for patients 12 years and older (AQLQ +12) score from baseline/DoR at week 52
- change in 6-item Asthma Control Questionnaire (ACQ-6) score from baseline/DoR at week 52
- change in total asthma symptom scores (day and night) from baseline at week 52
- percentage of asthma control days from baseline/DoR to week 52
- change in St. George's Respiratory Questionnaire (SGRQ) from baseline/DoR at week 32
- time to first clinical asthma exacerbation during the 52-week treatment period
- frequency of exacerbations requiring hospitalization or emergency department visits per patient during the 52-week treatment period
- frequency of moderate exacerbations defined as exacerbations requiring additional asthma controller medication that was not a systemic corticosteroid and that did not result in an asthma-specific hospitalization or emergency department visit during the 52-week treatment period

Testing of the secondary variables will be performed using the sequential testing procedure in the order as specified above, as described in Section 4.3.

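### A treatment completer seen 4 to 7 days early at week 52 has no week-52 symptom score, because the diary window is fixed at days 358-364 and later entries are excluded

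*SAP*

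**What the plan says.** The endpoint is "change in total asthma symptom scores (day and night) from baseline at week 52" (SAP 6.3.1), tested fourth among the secondary endpoints.

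- **Diary day.** Under SAP 4.5, "the day used for analysis will consist of the evening assessment for the day and the morning assessment for the following day". The note to Table 3 adds that "Study Day 1 denotes the first dose of study drug", and the table ends at Day 364.
- **Weeks.** "Weekly average data will be generated using 7-day windows derived based on these analysis days" (SAP 4.5).
- **Daily score.** "Total asthma symptom score (range: 0-9) will be derived as the sum of the daytime and nighttime symptom scores" (SAP 6.3.9.1.1), so a day needs both entries.
- **Minimum data.** "At least 4 of the 7 measurements need to be recorded for a week to be included in the analysis" (SAP 6.3.9.2). A week below that is missing and nothing is imputed. The change at each week is analysed by MMRM.
- **Visit window.** SAP Table 1 and Protocol Table 2 allow the week-52 visit at ±7 days.
- **End of data.** SAP 6.3 ends a completer's on-treatment period at the actual week-52 visit, and "Measurements collected outside of these defined timeframes will be excluded from the analyses". Protocol 3.16.3.1.2 also has the diary collected and reviewed at that visit.

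The other end of the change score is tied to an actual date: SAP 4.2.1 takes baseline from the 7 days before the day of randomization.

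**The concern.** The diary window for week 52 is fixed in calendar time from first dose, but the data stop at a visit that may fall up to a week earlier. Nothing visible in the SAP moves the window to the actual visit. The early-termination mapping in SAP 4.5 concerns visit assessments, and SAP 6.3.9.2 gives no fallback to the last available week.

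A patient who completes treatment, keeps a perfect diary and attends within the permitted window can therefore have no observed week-52 value, purely because of scheduling. The same early visit does supply week-52 values for FEV1, AQLQ +12 and ACQ-6, which come from the visit itself. At stake is the precision of one endpoint in the fixed sequence.

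**Working it through.** **1. Reproduce the plan's last diary day.** Week k covers diary days 7(k-1)+1 to 7k. For k = 52 this is 7×51+1 = 358 to 7×52 = 364, which matches the end of Table 3. The range 358-364 is not printed in the SAP; it follows from Table 3 and the 7-day windows.

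**2. Count usable days.** Take the nominal visit as study day 365 (day 1 plus 364 days), so the allowed window is days 358-372. A visit e days early falls on V = 365 - e. The last complete diary day is V - 1 (evening of V - 1, morning of V). Usable week-52 days = (V - 1) - 357 = 7 - e.

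| Days early (e) | Visit day | Usable days | Week 52 |
|---|---|---|---|
| 0 | 365 | 7 | kept |
| 1 | 364 | 6 | kept |
| 2 | 363 | 5 | kept |
| 3 | 362 | 4 | kept |
| 4 | 361 | 3 | missing |
| 5 | 360 | 2 | missing |
| 6 | 359 | 1 | missing |
| 7 | 358 | 0 | missing |

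Late visits lose nothing from days 358-364.

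**3. Vary the counting convention.**
- Nominal visit on study day 364: missing from 3 days early.
- No morning entry on the visit day: missing from 3 days early.
- Evening-only entry on the visit day counted as a measurement: missing from 5 days early.

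The cut-off moves, but the problem remains under each. Imperfect diaries add to it: at an assumed 90% daily completion, the chance of at least 4 days is 0.997, 0.984, 0.919 and 0.656 for e = 0 to 3.

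**4. Share of completers affected.** The documents give no distribution of visit dates, so this step rests on assumptions. For normal timing centred on day 365 and truncated to the window, the share is [Φ(-3.5/SD) - Φ(-7.5/SD)] / [Φ(7.5/SD) - Φ(-7.5/SD)]:
- SD 2 days: 4.0%
- SD 3 days: 11.7%
- SD 4 days: 17.1%
- Uniform over the 15 allowed days: 4/15 = 26.7%, an extreme case

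If all 225 patients per arm completed, the three normal cases correspond to about 9, 26 and 38 patients per arm.

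**5. Cost in precision.** As a simple approximation with two weeks, where week 51 is always observed and a fraction f lacks week 52, the variance of the week-52 mean is inflated by 1 + (1 - r²)f/(1 - f). The week-51/week-52 correlation r is assumed.

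| f | r = 0.8 | r = 0.9 |
|---|---|---|
| 4% | 0.36×0.04/0.96 = 1.5% | 0.19×0.04/0.96 = 0.8% |
| 12% | 0.36×0.12/0.88 = 4.9% | 0.19×0.12/0.88 = 2.6% |
| 17% | 0.36×0.17/0.83 = 7.4% | 0.19×0.17/0.83 = 3.9% |
| 27% | 0.36×0.27/0.73 = 13.3% | 0.19×0.27/0.73 = 7.0% |

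**The case against.** The strongest reply is that very little is lost. A visit on day 358, 359, 360 or 361 drops only 0, 1, 2 or 3 recorded diary days; the rest of the patient's last 7 days lie in week 51 (days 351-357), which is kept in full. A reader might infer that a complete final week is thrown away, or that the patient leaves the analysis. Neither is so: weeks 1-51 stay in the MMRM and inform the week-52 estimate. This stands, and it limits the harm to precision.

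Fixed windows also have a merit. They hold every diary week at the same time on treatment and handle late attendees without loss. Moving the week-52 window to the visit for everyone would discard a valid days 358-364 window after a late visit, and for a day-358 visit would enter the same 7 days as both week 51 and week 52. This also stands, and it restricts the remedy.

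Finally, parts of SAP 6.3.9.2 are redacted, so a further rule there cannot be excluded, although the visible sentences on weekly averages are complete. None of these replies gives an early-attending completer an observed week-52 value.

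**Conclusion.** The gap is real but modest. Under the visible rules, a completer seen 4 to 7 days early has no week-52 symptom score; the cut-off is 3 or 5 days under other counting conventions. With normal visit timing, about 4%, 12% or 17% of completers are affected for an SD of 2, 3 or 4 days. For 4-12% missing, variance rises by about 1-5% at assumed correlations of 0.8-0.9.

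Two stronger readings are not supported:

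- **Bias in the treatment comparison.** This would need early attendance to be related to arm or outcome, and nothing in the documents suggests that it is.
- **A loss of 27%, or 60 patients per arm (4/15 × 225).** This needs visits spread evenly over all 15 allowed days and every randomized patient to complete treatment.

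The primary endpoint is not touched. The point merits a change because the loss falls on a fixed-sequence endpoint and is cheap to avoid.

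**What to change.** Add a rule to SAP 4.5 and 6.3.9.2, before unblinding:

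- For patients who complete treatment and whose week-52 visit date leaves fewer than 4 possible diary days in days 358-364, the week-52 value is the mean of the last 7 complete diary days before that visit, with at least 4 recorded.
- Those days count towards week 52 only, so that no diary day enters both week 51 and week 52.
- All other patients, including late attendees, keep the fixed window of days 358-364.

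The trigger is the visit date, not how well the diary was kept, so low compliance alone does not move the window. With a complete diary, every early attendee then has 7 of 7 days.

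The cost is a short addition to the SAP and a small programming change. There are two downsides for these patients. Their final window ends up to a week earlier. Week 51 also becomes missing: at least 4 of its days move to week 52, leaving 3, 2, 1 or 0 for visits 4, 5, 6 or 7 days early. The missing week is thus moved from the tested time point to one that is not tested.
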